7.5.5.11. Hospital Attendance Questionnaire

Information on post-intervention hospital attendance rate will be collected using a hospital attendance questionnaire administered at six months and 12 months post-intervention. Participants will be asked to record the dates of all hospital visits (inpatient and outpatient visits) that they have attended since their intervention for events/conditions possibly associated with BPE, condition progression, intervention (including routine follow-up appointments post-intervention), along with the reason for each visit.

7.5.5.12. Catheterisation Questionnaire

Information on catheterisation use after the 12 months post-intervention visit will be collected using a catheterisation questionnaire administered at the two and three years post-intervention. Participants will be asked to confirm if they have had a catheter at any point since their last trial visit and if so, to provide the insertion and removal dates (if possible), along with the reason for each episode of catheterisation.

7.6. Pre-Procedure Checklist

A pre-procedure checklist will be completed by the operating surgeon on the day of intervention to check that the participant remains willing to participate in the trial and that they still meet the eligibility criteria. If the participant no longer meets the eligibility criteria, (e.g. the participant has developed urinary retention and has subsequently been catheterised), then they will be withdrawn from their allocated trial intervention and treated according to the standard of care procedures in place at their local site/UAN. Any concerns about continuing eligibility can be discussed with the CI.

Data will be collected by the operating surgeon via the completion of either a trial specific paper form or via the use of an electronic portal (method of collection determined by the operating site of each UAN).

7.7. Operative, Perioperative and Post-operative Parameters

This will encompass the collection of specified operative data by the operating surgeon and perioperative and post-operative data by the participant's research team, from the point of intervention up to 12 months post-intervention.

Operative parameter data collected by the operating surgeon will include: method of anaesthetic, name of operating surgeon, operative time, intraoperative adverse events, location of procedure, (e.g. theatre, urology clinic), where the patient is transferred to after the procedure, (e.g. home, day-case ward, recovery ward), equipment failure, number of intervention items used, change of procedure from original randomisation allocation (if required) and use of any blood products during surgery. As

described in section 7.7., surgeons will have the option of either completing a trial specific paper form or entering the data electronically.

Perioperative and post-operative data will be collected by the designated lead research team within the participant's trial site, up to and including the 12 months post-intervention visit. This will be obtained via discussions between the participant and the research team at the six weeks and six months post-intervention telephone visits and on-site one year post-intervention visit. Data collected will include:

- Use and duration of catheterisation (if applicable) perioperatively up to six weeks postintervention and then post-operatively up to and including 12 months post-intervention
- Use of any blood products up to six weeks post-intervention
- Incidents of acute urinary retention post-intervention up to and including 12 months post-intervention
- Details of any surgical re-intervention required (at the six months and 12 months postintervention visit) as reported in participant questionnaires

If necessary, the participant's medical notes should also be reviewed to aid collection of the required data.

7.8. Discharge Summary

Once the patient is discharged from hospital following their surgical intervention, a copy of the discharge summary letter will be sent to the designated lead research team within the participant's trial site. Discharge summary data will be entered into the trial database, this will include length of stay for health economic evaluation, as well as discharge medications.

7.9. Adverse Event Review

Participants will receive a telephone call from their designated lead research site at six weeks and six months post-intervention and will be asked to provide details of any adverse events they have experienced since their procedure. This will include details on any hospital attendance (both in-patient or out-patient) associated with BPE, condition progression, intervention or treatment failure, need for further medical input (either in secondary care or via GP), as well as details of any medications taken for adverse events. See section 9.0 for further information on safety reporting including protocol specific reporting exclusions.

7.10. Concomitant Medications

The use of prostate specific medications that are used for the treatment of male LUTS due to BPE is permitted although generally these drugs will be stopped after administration of the trial intervention. Certain other medications may need to be stopped as per local site protocol.

Only medications for the control/relief of the following conditions/events will be collected:

- urological symptoms
- pain relief following study intervention

- antibiotics to treat infections post study intervention
- anti-platelet and anti-clotting medication
- all medications associated with adverse events as defined in section 9.2.

Drug names, indications and start & end dates of concomitant medications for each participant will be collected during the trial by the research site staff at all visits between the on-site screening visit, and the on-site 12 months post-intervention visit.

7.11. Gift Vouchers

On return of the completed patient questionnaires at two and three years post-intervention, patients will be sent a gift voucher as a thank you for their participation.

7.12. Schedule of Events

	Screening	Baseline (within 3 months prior to procedure)	Procedure	6 weeks post- procedure (+/-1 week)	6 months post- procedure (+/- 1 month)	12 months post- procedure (+/- 1 month)	2 years post- procedure (+/- 1 month)	3 years post- procedure (+/- 1 month)
Туре	On-site	Remote	On-site	Remote + phone	Remote + phone	Remote + On-site	Remote	Remote
Consent (must be done prior to any assessments)	х							
Demographics and Medical History	х							
Prostate Volume	Хa							
Digital Rectal Exam	Хр							
Eligibility	х							
Randomisation	х							
Give out Post-Intervention Participant Diary	х							
Flow Test and Post Void Residual	Х°					x		
Pre-Procedure Checklist			х					
Operative Parameters			Χď					
Perioperative Parameters				х				
Post-Operative Parameters					х	х		
Discharge Summary			х					
Adverse Events			х	х	х			
Concomitant Medication	х		х	х	х	х		

	Screening	Baseline (within 3 months prior to procedure)	Procedure	6 weeks post- procedure (+/-1 week)	6 months post- procedure (+/- 1 month)	12 months post- procedure (+/- 1 month)	2 years post- procedure (+/- 1 month)	3 years post- procedure (+/- 1 month)
Туре	On-site	Remote	On-site	Remote + phone	Remote + phone	Remote + On-site	Remote	Remote
	1	Patient Rep	orted Outcom	nes (electronic or pa	per)		1	
Post-intervention catheterisation status					Xe	Xe	Х ^е	Хe
Re-intervention status					х	х	х	х
Hospitalisation Attendance Questionnaire					х	х		
Catheterisation Questionnaire							х	х
I-PSS inc Qol	X ^f	Χ ^f			х	х	х	х
EQ-5D-5L	X ^f	Χ ^f		х	х	х	х	х
Randomisation treatment choice				Х				
ICIQ-MLUTS	Χ ^f	Χ ^f			Х	x	Х	х
ICIQ-MLUTSsex	Χ ^f	Χ ^f			Х	х	х	х
ICIQ-LUTSqol	X ^f	Χ ^f			х	х	х	х
Healthcare Services	X ^f	Χ ^f			х	х	х	х
Time and Travel						х		
Acceptability Test					х			

^aWhere not available from standard of care within 12 months prior to consent

^bWhere cancer has not previously been excluded by either DRE, or MRI, or a negative biopsy within 12 months prior to consent.

To be done at screening if not measured in the previous six months prior to consent. Flow test and post void residual can **either** be completed at the end of the screening visit once eligibility has been confirmed (if this is convenient for both the patient and research team), or at a separate visit before the procedure within six weeks of screening, if more convenient.

dFor completion both pre- and post-surgery.

elf patient is catheterised at this timepoint then the following PROMS should not be completed; I-PSS, I-PSS-QOL and ICIQ-MLUTS

fScreening PROMS must be completed prior to randomisation. In the event that the time between completing the questionnaires and receiving the intervention is greater than six months, the questionnaires will need to be repeated within three months prior to the procedure.

7.13. Withdrawal and Discontinuation

The investigator may discontinue a participant from their allocated trial intervention or withdraw them from the trial at any time if the investigator considers it necessary. Advice from the Chief Investigator should be sought where needed. The participant may also discontinue from aspects of the study or withdraw consent to continue in the study at any time. See the relevant criteria below. The reason for discontinuation or withdrawal should be documented in the trial database eCRF and the participant's medical notes.

7.13.1. Withdrawal Criteria

Participants have the right to withdraw from the trial at any time without having to give a reason. The investigator should complete an investigator led withdrawal form on behalf of the participant. If available, the reason for withdrawal should be documented on the paper withdrawal form, the trial database eCRF and the participant's medical notes. Participants who withdraw from the trial will not be replaced.

If a trial participant withdraws from the trial, all data collected up to the point of withdrawal will be retained and included in the analysis. Routine NHS data will also be collected for the trial up to the three year visit timepoint, unless a participant asks for this to stop. Consent for this will be sought on the withdrawal form. A list of possible routine data to be collected is described in the Operative, Perioperative and Post-Operative Parameters section 7.8

Discontinuation from an aspect(s) of the study (as per section 7.14.2.) is preferable to a withdrawal however, in situations where this is not appropriate or feasible, the Investigator can decide to withdraw the participant entirely. Reasons for an Investigator led withdrawal can include an adverse event that renders the participant unable to continue in any aspect of the trial, or where the participant is unable to comply significantly with trial requirements. Advice from the Chief Investigator should be sought where needed.

When an investigator withdraws a participant from the trial they should also complete an investigator led withdrawal form. The participant must be informed of the investigator decision and their return to their routine care pathway in the NHS.

7.13.2. Discontinuation criteria

If a randomised participant declines their allocated intervention, they can remain in the trial and complete all follow-up visits as part of the intention to treat analysis, as long as the patient is willing to be followed up as per the study requirements. If an intervention date had not been scheduled (and no alternative trial intervention is performed) then follow-up timepoints should be measured from the date of randomisation. In all cases, it should be documented in the trial database eCRF and the participant's medical notes that they have declined their randomised intervention. This would not be considered a withdrawal of consent but would be regarded as a discontinuation of their allocated intervention.

If a randomised participant does not want to attend any follow-up visits but is willing to continue to complete the trial questionnaires (or vice versa), they may continue in the study. This would not be

considered a withdrawal of consent but would be regarded as a discontinuation of an aspect of the trial follow-up.

All participant discussions regarding any aspect of discontinuation should be clearly documented in the patient notes, with ongoing consent for the study documented when necessary. It is possible, due to the period of time between consent and surgery, some participants may no longer meet the eligibility criteria at the time of the intervention. As stated in section 7.7., a pre-procedure checklist will be completed by the operating surgeon on the day of intervention to check that the participant remains willing to participate in the trial and still meets the eligibility criteria. If the participant no longer meets the eligibility criteria, then they will be discontinued from their allocated trial intervention and treated according to the standard of care procedures in place at their site. They may still continue with the trial follow-up if they are willing. Follow-up timepoints should be measured from the planned date of intervention.

7.14. End of Trial

The trial will end after the last patient's last visit (data collection timepoint).

7.15. Post Trial Care

At the end of their participation in the study participants will continue to receive standard NHS care. Where a participant has been referred from a PIC site, they may remain under the care of the team at the research site hospital trust for standard care follow up post intervention.

8. TRIAL INTERVENTION

Participants will receive one of the following interventions:

- I. Prostatic urethral lift (PUL)
- II. Rezum
- III. Temporary Implantable Nitinol Device (iTIND)
- IV. TURP

Please see section 2. Rationale.

8.1. Training and Competence

All participating surgeons will have completed a mandated training pathway, including at least 10 cases for PUL and Rezum, and five cases for iTIND since completing training. Confirmation of completion of these minimum case numbers should be recorded on the trial surgical training log prior to the surgeon performing any MIT as part of the PREMISE trial. Additionally, we will record the number of cases performed by each surgeon for each MITS in their career prior to their participation in the PREMISE trial, allowing for further analysis of surgeon experience. During the trial we will record details of which surgeon performs each procedure, and the total, by surgeon, for each.

A surgeon in training may perform the procedure or part of it, provided that they are under the direct supervision of a surgeon who has completed the above mandated training pathways and who has been appropriately delegated the task of performing the procedure by the PI (as documented via the delegation log).

8.2. Known Risks

Please see Assessment of Expectedness in section 9.3.3 for list of potential side effects for each intervention.

9. SAFETY REPORTING

9.1. Definitions

Term	Definition		
Adverse Event (AE)	Any untoward medical occurrence in a participant, including occurrences which do not necessarily have a causal relationship with the study procedures/intervention		
Adverse Reaction (AR)	An AE where there is evidence to suggest there is a causal relationship between the event and the study procedures/intervention.		
Serious Adverse Event	Any untoward medical occurrence that:		
(SAE)	Results in death		
	Is life-threatening*		
	 Requires inpatient hospitalisation or prolongation of existing hospitalisation 		
	 Results in persistent or significant disability/incapacity 		
	 Consists of a congenital anomaly or birth defect 		
	 is otherwise considered medically significant by the investigator 		
	* - life-threatening refers to an event in which the participant was at immediate risk of death at the time of the event; it does not refer to an event which hypothetically might have caused death if it were more severe.		
Related Serious Event	An SAE where there is evidence to suggest there is a causal relationship between the event and the study procedures/intervention.		
Unexpected Related Serious Event (URSE)	An SAE where there is evidence to suggest there is a causal relationship between the event and the study procedures/intervention, where the event is unexpected		

9.2. Adverse Events

9.2.1. Recording Adverse Events

It is intended that all AEs occurring from the point of surgical intervention until six months postsurgery possibly associated with BPE, condition progression, intervention or treatment failure are collected as adverse events. These events must be recorded in the trial database eCRF and recorded in the participant's medical notes as part of their ongoing care. The Clavien Dindo criteria in section 9.2.3. should be used for Assessment of Severity.

All intraoperative AEs will be recorded and identified via a question in the Operative Parameters form and post-operative AEs will be patient reported by an adverse events questionnaire administered at the telephone call at six weeks and six months post-surgery or identified through medical records.

The documentation of each AE should include an event term, event duration (start and stop dates) and details of any action taken or treatment in response to the event. Each AE must be assessed by the site PI or delegated investigator for severity (section 9.2.3.), seriousness (section 9.2.4.) and causality (section 9.2.5.).

9.2.2. Exclusions to Adverse Events reporting

For the purposes of this trial, AEs not related to the condition or the intervention will not be collected, including but not limited to hospitalization for the non-related conditions.

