3. OBJECTIVES AND OUTCOME MEASURES

	Objectives	Outcome Measures
Primary	To compare the clinical effectiveness of 3 minimally invasive treatments (MITS) to transurethral resection of prostate (TURP) for treatment of bladder outlet obstruction (BOO) due to enlarged prostate over 12 months	Change in international prostate symptom score (I-PSS) from baseline to 12 months post-intervention

Primary Economic	To compare the cost effectiveness of 3 minimally invasive treatments (MITS) to transurethral resection of prostate (TURP) for treatment of bladder outlet obstruction (BOO) due to enlarged prostate	Incremental cost per quality-adjusted life year (QALY) gained at 12 months post-intervention Cost-effectiveness acceptability curves (CEACs) to assess the probability of each of the interventions being considered cost-effective at different willingness-to-pay (WTP) thresholds for a gained QALY QALYs will be calculated using responses to the EQ-5D-5L questionnaire
Secondary	To compare impact on bladder voiding efficiency (BVE) and maximum flow rate (Qmax)	Change from baseline to 12 months post-intervention in: Post void residual Maximum flow rate (Qmax)
	To compare incidence of adverse events	Adverse events up to six months post- intervention collected via: Operative parameters Adverse event review at six weeks and six months post-intervention
	To compare impact on incontinence	International Consultation on Incontinence Questionnaire Male Lower Urinary Tract Symptoms Module (ICIQ-MLUTS) at baseline, six months, 12 months, two and three years post-intervention
	To compare impact on sexual function	ICIQ-MLUTSsex at baseline, six months, 12 months, two and three years post-intervention
	To compare impact on quality of life and general health	I-PSS-QOL at baseline, six months, 12 months, two and three years post- intervention
		 ICIQ-LUTSqol at baseline, six months, 12 months, two and three years post- intervention
		EQ-5D-5L at baseline, six weeks post- intervention, six months, 12 months, two and three months post-intervention
	To establish the most suitable outcome measure for the context of male LUTS intervention	Correlation of I-PSS / ICIQ-MLUTS

	To assess the impact of urinary and sexual symptoms on quality of life	Correlation of overall QOL (ICIQ-LUTSqol) with symptom scores from ICIQ-MLUTSsex and I-PSS questionnaires
	To compare the amount of time spent in hospital post-intervention	Length of post-intervention hospital stay

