9.2.5. Assessment of Causality

The relationship between the intervention and the occurrence of each AE must be assessed and categorised by the PI or delegated clinician using clinical judgement to determine the causal relationship. Other factors such as medical history of underlying diseases, concomitant therapy and any other relevant risk factors should be considered. The assessor should also consult the expected events in section 9.3.1. If there is any doubt, the CI may be consulted. The following definitions should be used:

Yes (related) The event is considered related or possibly related to the

intervention

No The event is not considered related to the intervention

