9.3. Expedited Safety Reporting

The safety profile of the four interventions is well-established within this patient population and a list of expected events can be found in section 9.3.3. Immediate reporting of expected SAEs to the Sponsor is not required, only unexpected SAEs related to the intervention require expedited safety reporting. All adverse events (including expected and unexpected SAEs) should be recorded in the eCRF (Sealed Envelope) and will be reviewed by the Data Monitoring Committee on a regular basis (see section 13.1).

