9.3.4. Safety Reporting Summary Table

Event	Required actions	
Adverse Event	Record in eCRF	
SAE that is related to BPE, condition progression or treatment failure	Record in eCRF and mark as serious	
SAE that is related to the intervention and is expected (as per protocol section 9.3.1)	Record in eCRF and mark as serious	
SAE that is related to the intervention and is unexpected (as per protocol section 9.3.1)	Record in eCRF and mark as serious Report immediately to NCTU as a suspected URSE on an SAE Report Form via secure email	
(Serious) Adverse Event not related to intervention, BPE, condition progression or treatment failure	None (will not be collected for this study)	

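### Post-operative adverse events, including serious events and deaths, enter the data only after an open-label judgement of possible association, which risks unequal ascertainment between arms; section 9.3 must be reconciled with 9.2.2 and 9.3.4

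*Protocol*

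**What the plan says.** Protocol section 3 lists among the secondary objectives "To compare incidence of adverse events", with events collected to six months after the intervention. Section 4 states that participant, surgeon and clinical team cannot be blinded.

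Section 9.2.1 limits collection to events "possibly associated with BPE, condition progression, intervention or treatment failure are collected as adverse events". It makes one clear exception: "All intraoperative AEs will be recorded and identified via a question in the Operative Parameters form". Section 9.2.2 states the exclusion: "AEs not related to the condition or the intervention will not be collected, including but not limited to hospitalization for the non-related conditions". The summary table in 9.3.4 gives the action for an adverse event, serious or not, that is unrelated to any of the four causes: "None (will not be collected for this study". Section 9.3.2 keeps unrelated serious events, including deaths, out of SAE reporting, and 9.5 keeps such deaths out of the eCRF.

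Under 9.2.1 and 9.2.5 the site investigator or a delegate assesses the causality of each event "using clinical judgement to determine the causal relationship", and possibly related counts as related.

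Two other places read more widely. Section 9.1 defines an adverse event without requiring a causal link. Section 9.3 says: "All adverse events (including expected and unexpected SAEs) should be recorded in the eCRF", for regular review by the Data Monitoring Committee (DMC). In the six-week and six-month calls of section 7.9, participants "will be asked to provide details of any adverse events they have experienced since their procedure", although that section then points to the exclusions in section 9.

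**The concern.** Relatedness is normally recorded as an attribute of an event already in the database. Here, for post-operative events, it decides whether the event is recorded at all. In an open-label trial the person deciding knows which procedure was done. If the same event is more readily linked to one procedure than to another, the recorded incidence differs between arms even when the true incidence does not. Both the secondary comparison and the DMC's view of safety rest on those records.

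The events most exposed are those whose link to the procedure is a matter of opinion: cardiovascular, thrombo-embolic and respiratory events in men aged 50 or over. The anaesthesia list in 9.3.3 includes deep vein thrombosis, pulmonary embolus, heart attack, stroke and chest infection. Section 2 says that the minimally invasive treatments (MITs) need general or regional anaesthesia less often than TURP does. An assessor therefore has grounds to weigh the same event differently by arm.

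**Working it through.** The plan gives no figure for attribution, so the main check is textual.

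**Step 1: which events pass through the filter**

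| Event | Rule | Filtered? |
|---|---|---|
| Intraoperative AE | 9.2.1 | No |
| Post-operative non-serious AE to six months | 9.2.1, 9.2.2 | Yes |
| Post-operative SAE to six months | 9.3.2, 9.3.4 | Yes |
| Death | 9.3.2, 9.5 | Yes |
| Transfusion, acute retention, catheter use, surgical re-intervention | 3, 7.7 | No; separate outcomes |
| Hospital attendance | 3, 7.3, 7.5.5.11 | Yes, a similar test of possible association |

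Deaths are not exempt. Of the separately collected outcomes, none captures a cardiovascular, thrombo-embolic or respiratory event as such.

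**Step 2: who applies the filter.** Section 9.2.1 names the investigator or delegate as assessor of causality. It does not say who decides whether an event reported by telephone is entered. That unblinded site staff decide is an inference, but a reasonable one, because the research site makes the calls (7.9) and no blinded adjudication is described.

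**Step 3: the threshold.** Section 9.2.1 uses possible association with any of four causes. Sections 9.2.2 and 9.3.4 speak only of events not related and drop the word 'possibly'. Section 9.3 states no restriction. A site could record an unrelated SAE under 9.3 or leave it out under 9.3.4.

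**Step 4: what a difference in attribution would do (illustration only).** Let p be the true event rate, the same in both arms, and let s be the share of events that pass the filter.

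Recorded rate = p × s, so recorded risk ratio (MIT/TURP) = s(MIT) / s(TURP). The true rate cancels.

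All pass rates below are assumed. Counts also assume p = 5% and use the 134 men per intervention per comparison in section 10.2, giving 134 × 0.05 = 6.7 true events per arm.

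| s(TURP) | s(MIT) | Recorded counts per 134 (TURP, MIT) | Ratio |
|---|---|---|---|
| equal | equal | equal | 1.00 |
| 0.95 | 0.85 | 6.4, 5.7 | 0.85/0.95 = 0.89 |
| 0.95 | 0.75 | 6.4, 5.0 | 0.75/0.95 = 0.79 |
| 0.90 | 0.60 | 6.0, 4.0 | 0.60/0.90 = 0.67 |

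Swapping the arms gives the reciprocals: 0.95/0.85 = 1.12, 0.95/0.75 = 1.27 and 0.90/0.60 = 1.50. For plainly urological events s should be close to 1 in every arm, and the ratio close to 1.

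**The case against.** The strongest reply is that the filter is wide and its exceptions matter. It admits anything possibly associated with any of four causes. All intraoperative events are recorded, and several complications most specific to these procedures are outcomes in their own right. Restricted collection is a deliberate choice in a trial rated Type A for risk (2.1), whose procedures are said in 9.3 to have a known safety profile. The wording in 9.3 can be read as covering only the events that 9.2 defines, and 7.9 refers to the exclusions. This narrows the point to post-operative events whose cause is arguable. It does not remove it, because a wide filter can still be applied unequally, and 9.3 as written does not carry the limit.

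Three stronger readings are tempting, and the documents support none of them.

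- A reader might infer that events count after TURP and vanish after an MIT. Attribution of 60% against 20% would turn a true 5% into 3.0% and 1.0%, a threefold ratio. No attribution rates are given. The anaesthesia list is shared by all four procedures and assessors are told to consult the expected events. Section 2 allows iTIND under general anaesthetic, and sites might blame a newer device more readily. The leaning could go either way.
- A reader might infer that excluded events leave no trace. The Healthcare Services questionnaire (7.5.5.7) asks for each primary and secondary care visit and its reason. Section 7.10 collects anti-platelet and anti-clotting drugs with indications to 12 months, and consent covers notes review (7.1.2). This is only a partial cross-check: the questionnaire is patient-reported, lacks assessed severity and causality, and is planned for the economic evaluation.
- A reader might conclude that all-cause SAEs should be the main safety comparison. Unrelated illness in older men could dilute procedural differences, so that is a debatable trade-off.

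**Conclusion.** The point holds as a risk of differential ascertainment of unknown size and direction. It rests on three things: the text makes possible association a condition of entry for post-operative events, SAEs and deaths included; adverse-event incidence is compared between arms; and, by inference, unblinded site staff apply the condition. Bias is not shown. It would be nil in relative terms if the arms passed the filter equally, and the ratios of 0.67 to 0.89, or their reciprocals, only show what moderate assumed differences would do. At the assumed 5% true rate this is about two men per 134 or fewer.

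Separately, and whatever view is taken on bias, 9.3 does not agree with 9.2.2 and 9.3.4. The change is worth making because it is cheap and because these events are hard to reconstruct fully afterwards.

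**What to change.** In 9.2.1, 9.2.2, 9.3.2, 9.3.4 and 9.5, require that every serious adverse event, deaths included, from the procedure to six months is recorded in the eCRF whatever its cause, with relatedness as a field. Report all-cause SAEs by intervention alongside related SAEs. Reword 9.3 so that it states which events are recorded, in agreement with 9.2.2 and 9.3.4.

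Keep the filter of possible association for non-serious events, the exclusion of planned admissions for the study procedure, and the expedited-reporting rules as they are.

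The calls at six weeks and six months are already scheduled and medical records are already a source, so no visits and no additional 24-hour reports are needed. The cost is some extra eCRF entries for unrelated serious events, and some background noise in the all-cause table.
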